1.3. Number of Patients

Approximately 700 patients will be randomised globally in a 1:1 ratio (AZD9291: placebo) to this study. The primary endpoint of the study is DFS based on investigator assessment. DFS will first be tested in the subset of patients with Stage IIA-III A cancer. If statistical significance is shown for DFS in the subset of patients with Stage IIA-III A cancer, then it will be tested for the overall population with the test mass split between first and second analyses.

The primary analysis of DFS will occur when approximately 247 disease recurrence events have been observed in approximately 490 patients who are in Stage IIA-III A (i.e. non-IB). If the true DFS hazard ratio (HR) for the comparison of AZD9291 versus placebo in this patient population is 0.70, 247 disease recurrence events will provide 80% power to demonstrate a statistically significant difference in DFS at a 5% two-sided significance level (translating to an improvement in median DFS from 40 months to 57 months, assuming DFS is exponentially distributed). The minimum DFS HR that would be statistically significant (i.e. $p < 0.05$, two-sided) is 0.78.

If the true DFS HR for the comparison of AZD9291 versus placebo in the overall population is 0.70, 314 disease recurrence events will provide approximately 90% power to demonstrate a statistically significant difference in DFS at a 4% two-sided significance level (translating to an improvement in median DFS from 46 months to 66 months, assuming DFS is exponentially distributed). The minimum DFS HR that would be statistically significant (i.e. $p < 0.04$, two-sided) is 0.79.

At the time of the primary analysis it is anticipated that approximately 195 OS events (28% maturity) will have occurred (assuming a median OS of 96 months for the placebo arm) in the overall population. If the true OS HR for the comparison of AZD9291 versus placebo is 0.66, 195 death events provide approximately 80% power to demonstrate a statistically significant difference at the 4% (two-sided) significance level. With 195 death events and assuming a true OS HR of 0.85 there is approximately 90% chance of observing an HR < 1.02 .

Assuming 28 months non-linear recruitment the data cut-off for the primary analysis is estimated to occur approximately 68-70 months after first patient randomised.

It is estimated that 3200 patients will be screened in order to randomise 700 patients.

2. ANALYSIS SETS

2.1. Definition of Analysis Sets

2.1.1. Full Analysis Set

The full analysis set (FAS) will include all randomised patients.

The FAS will be used for all demographic summaries and efficacy analyses, and treatment groups will be compared on the basis of randomised study treatment, regardless of the treatment actually received.

2.1.2. Safety Analysis Set

The safety analysis set will consist of all patients who received at least one dose of study treatment.

Safety data will not be formally analysed but summarised using the safety analysis set, according to the treatment received; i.e. erroneously treated patients (e.g. those randomised to treatment A but actually given treatment B) will be summarised according to the treatment they actually received. If a patient received both treatments, then they will be summarised according to the active treatment.

2.1.3. Pharmacokinetic Analysis Set

The PK analysis set is defined as patients in the safety analysis set who received AZD9291 and have at least one measurable PK concentration, supported by the relevant date and time of this sample. For each time a PK sample was taken from a patient, the dosing data for that day and for multiple dosing, the dose date for the two days prior to the sample days must be available. For any individual sample from a patient to be included in the PK analysis set, the full sample data and dosing data need to be present for that sample/patient.

The pharmacokineticist will agree to the strategy for dealing with data affected by protocol deviations before any formal statistical analysis is performed. Protocol deviations may include changes to the procedures that may impact the quality of the data or any circumstances that can alter the evaluation of the PK. Examples may include but are not limited to: vomiting following oral dosing occurring within the timeframe of 2 times the median time after administration of a drug when the maximum plasma concentration is reached when the rate of absorption equals the rate of elimination (t_{max}); sample processing errors that lead to inaccurate bioanalytical results; incomplete dose administered; incomplete PK profile collected; and/or use of disallowed concomitant medication. In the case of a relevant protocol deviation or event, affected PK data collected will be excluded from the summaries and statistical analyses, but will still be reported in the study result listings. Any exclusions will be detailed in the CSR.

2.2. Protocol Violations and Deviations

Important protocol deviations are defined as those deviations from the protocol likely to have an impact on the perceived efficacy and/or safety of study treatments.

A list of important protocol deviations and any action to be taken regarding the exclusion of patients or affected data from specific analyses are defined in [Table 1](#) below and a list of deviations that are regarded as important are in [Table 2](#) below.

Note that the contents of these tables are not an exhaustive list. A complete list of anticipated protocol deviations (including important protocol deviations) will be compiled separately and finalised prior to unblinding. Note a longer list of important protocol deviations may be used for the IDMCs.

Table 1 Protocol Deviations with Action to be Taken for Analysis

Protocol Deviation	Action to be Taken for Analysis
Patient randomised and did not receive any study medication	Exclude from the Safety analysis set
Patient was given incorrect study medication	Analyse “As-randomised” for the FAS. Analyse “As-treated” for the Safety analysis set. If only the incorrect study medication was taken for the whole study, then analyse according to treatment taken. If patient received both AZD9291 and Placebo then analyse according to active treatment.

Table 2 Important Protocol Deviations

Criteria Type	Important Deviation Description
Inclusion Criteria	
 • Lack of Histologically confirmed diagnosis of primary non-small lung cancer (NSCLC) on predominantly non-squamous histology. • MRI or CT scan of the Brain was not done before randomization. • Non-Japanese Sites' patients with pathology at diagnosis: Post Surgery the AJCC Stage (7th edition) for the patient is not Stage IB, II or IIIA. • Japanese Sites' patients with pathology at Diagnosis: Post Surgery the AJCC Stage for the patient is not Stage II or IIIA. • No confirmation that the tumour harbours an EGFR mutation known to be associated with EGFR TKI (tyrosine kinase inhibitor) sensitivity (including Ex19del and L858R). • Not complete surgical resection of the primary NSCLC, and all surgical margins of resection not negative for tumour.
Exclusion Criteria	
 • Any anti-cancer therapy as follows: 
 • Prior treatment with neoadjuvant or adjuvant EGFR-TKI. • Pre-operative (neo-adjuvant) platinum based or other chemotherapy.

Table 2 Important Protocol Deviations

Criteria Type	Important Deviation Description
	
 • Pre-operative or post-operative or planned radiation therapy for the current lung cancer. • Any other prior anticancer therapy, including investigational therapy, for treatment of NSCLC other than standard platinum based doublet post-operative adjuvant chemotherapy. • Treatment with an investigational drug within five half-lives of the compound or any of its related material, if known. • Past medical history of ILD, drug-induced ILD, radiation pneumonitis which required steroid treatment, or any evidence of clinically active ILD.
IP Administration/ Study Treatment	
 • Patient was randomized but did not receive any treatment • Patient received medication in error e.g. patient dosed but not fully eligible for study treatment or patient received the incorrect treatment e.g. did not receive the treatment they were randomised to. • Patients with corneal ulceration and/or ILD who resume study treatment.
Procedures/Tests	
 • Baseline disease assessment performed more than 28 days prior randomization i.e. not performed during screening window. • Disease Recurrence scans not performed in accordance with the protocol time schedule RELATIVE to RANDOMISATION date or not at all.
Disallowed Medications	
 • Patient receiving anti-cancer therapies (e.g. anticancer drugs, radiotherapy) or other concomitant strong CYP3A inducers or herbal medications which are strong CYP3A inducers during the study, other than IP.

The following summary will be provided:

- A summary of the number and percentage of patients with an important protocol deviation by treatment group and overall and by type of deviation (Analysis set: FAS)

A by-patient listing of important protocol deviations will be provided in the CSR.

3. PRIMARY, SECONDARY AND EXPLORATORY VARIABLES

3.1. General Variables

3.1.1. Study Day Definitions

For the purpose of data summaries based on the full analysis set, for example efficacy, Study Day 1 is defined as the date of randomisation to study treatment. For visits (or events) that occur on or after randomisation, study day is defined as:

date of visit (or event) – date of randomisation + 1.

For visits (or events) that occur prior to randomisation, study day is defined as:

date of visit (or event) – date of randomisation.

There is no Study Day 0.

For the purpose of the safety data summaries, and any summaries based on the safety analysis set, Dose Day 1 is defined as the date of first dose of study treatment (referred to in the protocol as Week 1 Day 1). For visits (or events) that occur on or after first dose, dose day is defined as:

date of visit (or event) – date of first dose of study treatment + 1.

For visits (or events) that occur prior to first dose, dose day is defined as:

date of visit (or event) – date of first dose of study treatment.

There is no Dose Day 0.

For listings (such as for adverse events [AEs]) that include the derivation of “days since last dose”, this is defined as:

event date – date of last dose.

Events that occur on the same day as the last dose of study treatment will therefore be described as occurring zero days from the last dose of study treatment.

3.1.2. Visit Windows

For summaries of vital signs, laboratory data, digital ECG, and HRQoL, etc., assessments will be assigned to calculated visit windows (using study day).

The time windows should be exhaustive so that data recorded at any time point has the potential to be summarised. Inclusion within the visit window should be based on the actual date and not the intended date of the visit. For summaries at a patient level, all values should be included, regardless of whether they appear in a corresponding visit based summary, when deriving a patient level statistic such as a maximum.

The window for the visits following baseline (including unscheduled visits) will be constructed in such a way that the upper limit of the interval falls half way between the two visits.

For summaries showing the maximum or minimum values, the maximum/minimum value recorded on treatment will be used (regardless of where it falls in an interval). Listings should display all values contributing to a time point for a patient; they should also highlight the value for that patient that was used in the summary table, wherever feasible.

For visit-based summaries:

- If there is more than one value per patient within a visit window then the closest to the planned study day value should be summarised, or the earlier in the event the values are equidistant from the planned study day. The visit will be missing if no assessment was reported within the specified visit window around the planned study day.
- To prevent very large tables or plots being produced that contain many cells with meaningless data, summary statistics will be presented where at least 10 patients in either treatment group have data recorded at a particular visit. If there are assessments which fall in to a window for a visit that is not scheduled, summary statistics will be presented if at least 10 patients in either treatment group have data recorded for that visit.

3.1.3. Handling Missing Data

In general, other than for partial dates, missing data will not be imputed and will be treated as missing, unless otherwise specified.

3.1.3.1. Imputation of partial dates

Concomitant Medication and Adverse Events Start Dates

- If year is missing (or completely missing), do not impute.
- If (year is present and month and day are missing) or (year and day are present and month is missing), impute as January 1st.
- If year and month are present and day is missing, impute day as first day of the month.

Concomitant Medication and Adverse Events End Dates

- If year is missing (or completely missing), do not impute.
- If (year is present and month and day are missing) or (year and day are present and month is missing), impute as December 31st.
- If year and month are present and day is missing, impute day as last day of the month.

In addition for AEs, if for a partial start date the AE start date could (when also considering the AE end date) potentially be on the first study treatment date, the AE start date will be imputed with the first study treatment date to assume a “worst case” scenario; e.g. AE from UNK-Feb-2014 to 23-Mar-2014 with first study treatment date 21-Feb-2014, then the AE start date will be imputed to 21-Feb-2014.

Death Dates

- If a patient is known to have died where only a partial death date is available then the date of death will be imputed as the latest of the last date known to be alive +1 from the database and the death date using the available information provided:
 - a. For Missing day only – using the 1st of the month
 - b. For Missing day and Month – using the 1st of January

If there is evidence of death but the date is entirely missing, it will be treated as missing, i.e. censored at the last known alive date.

Diagnostic Dates

For missing diagnostic dates, if day and/or month are missing use 01 and/or Jan. If year is missing, put the complete date to missing.

3.1.4. Imputation Rules for Lab Values Outside of Quantification Range

Lab values below the lower limit of quantification (LLoQ) that are reported as “<LLoQ” or “≤LLoQ” in the database will be imputed by $LLoQ \times 0.99$ for analysis purposes. The original value will be listed.

Lab values above the upper level of quantification (ULoQ) that are reported as “>ULoQ” or “≥ULoQ” in the database will be imputed by $ULoQ \times 1.01$ for analysis purposes. The original value will be listed.

3.1.5. Imputation rules for SF-36v2

Imputation rules will be implemented per user’s manual for SF-36V2 Health Survey, third edition.

3.2. Efficacy Assessments

3.2.1. Disease Free Survival

DFS is defined as the time (in days) from the date of randomisation until the date of disease recurrence or death (by any cause in the absence of recurrence) regardless of whether the patient withdraws from randomised therapy or receives another anti-cancer therapy prior to recurrence (i.e. date of DFS event or censoring – date of randomisation + 1).

Patients who are disease-free and alive at the time of analysis will be censored at the date of their last assessment for disease recurrence. However, if the patient recurs or dies immediately after two or more consecutive missed visits, the patient will be censored at the time of the latest evaluable assessment for disease recurrence prior to the two missed visits. Given the scheduled visit assessment scheme (i.e. twelve-weekly for the first 24 weeks and then twenty-four-weekly thereafter) the definition of 2 missed visits will change. If the previous assessment is less than study day 78 (i.e. week 11) then two missing visits will equate to 25 weeks since the previous assessment, allowing for late visit (i.e. 2×12 weeks + 1 week for a late assessment = 25 weeks). If the two missed visits occur over the period when the scheduled frequency of assessments changes from twelve-weekly to twenty-four-weekly this will equate to 38 weeks (i.e. take the average 12 and 24 weeks which gives 18 weeks and then 2×18 weeks + 1 week of an early assessment + 1 week for a late assessment = 38 weeks). The time period for the previous assessment will be from study days 78 to 161 (i.e. week 11 up to week 23). If the previous assessment is from week 23 (day 162) onwards (when the scheduling

changes to twenty-four weekly assessments), two missing visits will equate to 50 weeks (i.e. 2 x 24 weeks + 1 week for an early assessment + 1 week for a late assessment = 50 weeks).

If the patient has no evaluable visits or does not have baseline data (chest, abdomen & brain scans), they will be censored at Day 1 unless they die within two visits of baseline (24 weeks plus 1 week allowing for a late assessment within the visit window) in which case the event will be used.

The DFS time will always be derived based on scan/assessment dates and not visit dates. If assessments contributing towards a particular visit are performed on different dates, for example, a biopsy confirming disease recurrence following the scan where recurrence was suspected, the date of recurrence will be the earliest of the dates of the assessment that triggered the recurrence. When censoring a patient for DFS the patient will be censored at the latest of the dates contributing to a particular overall visit assessment.

DFS rate at 6 months (i.e. 182.625 days), 12 months (i.e. 365.25 days), 18 months (i.e. 547.875 days), 24 months (i.e. 730.5 days), 36 months (i.e. 1095.75 days), 48 months (i.e. 1461 days) and 60 months (i.e. 1826.25 days) is defined as the proportion of patients alive and disease free at the timepoint, estimated from Kaplan-Meier (KM) plots of the primary endpoint of DFS at the time of the primary analysis.

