4.2 Treatment period

Patients will be randomised at Visit Day1 and receive either AZD9291 or matching placebo. Patients will take the first dose of study drug within 2 days of randomisation and will continue treatment until recurrence of disease, treatment discontinuation criterion is met or treatment is completed. The treatment duration period is 3 years (156 weeks), except for patients who receive open-label osimertinib after recurrence and continue until subsequent progression or another one of the situations described in Section 3.10.

The assessments required during the treatment period are detailed in the Study Plan [\(Table 1\)](#).

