5.1 Efficacy assessments

5.1.1 Disease-free survival

Disease-free survival is the primary endpoint in this study and is defined as the time from the date of randomisation until the date of disease recurrence or death from any cause in the absence of disease recurrence. Disease recurrence is defined as evidence of disease recurrence on CT or MRI scan and/or pathological disease on biopsy by investigational site assessment.

The imaging modalities used for radiological assessments will be CT scans of the chest and abdomen (including liver and adrenal glands) with contrast. In the rare case where a patient is intolerant of the contrast medium the preferred imaging would be CT chest without contrast and MRI abdomen with contrast; however a non-contrast abdominal CT will also be accepted. The methods used at baseline (CT or MRI) must be used at each subsequent follow-up assessments. A pre-surgical MRI or contrast CT scan of the brain is considered standard of

care and must be done prior to surgery. Patients in whom this was not done prior to surgery may still be enrolled providing that appropriate imaging is performed prior to randomisation. Any other sites where disease is suspected at baseline must also be imaged to confirm absence of disease prior to randomisation into the study. The baseline assessments should be performed within 28 days prior to study drug initiation. Subsequent assessments are to be performed at 12 week, 24 week and then every 24 weeks until 5 years (264 weeks), and then yearly thereafter relative randomisation, until disease recurrence is recorded. If a patient discontinues treatment prior to disease recurrence or receives other anti-cancer treatment, patient should continue to be imaged in accordance with this schedule until disease recurrence is noted. It is important to follow the assessment schedule as closely as possible. If scans are performed outside of the scheduled visit (\pm 7 days window interval) and the patient has not recurred, every attempt should be made to perform the subsequent scans at their scheduled time points. Any other sites at which a new disease is suspected should also be appropriately imaged during the study.

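### The 25-week two-missed-visits limit for DFS is counted from the baseline scan, so missing only the week-12 scan can censor a recurrence found on time at week 24

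*SAP*

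**What the plan says.** SAP 3.2.1 censors a patient whose recurrence or death directly follows at least two successive missed visits. Censoring is at the last evaluable scan before the gap. Because the scan interval changes over time, the SAP defines two missed visits by elapsed time in three branches:

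- **Previous scan before study day 78:** "then two missing visits will equate to 25 weeks since the previous assessment, allowing for late visit". The arithmetic is 2 x 12 weeks plus "1 week for a late assessment = 25 weeks".
- **Previous scan on days 78 to 161:** 38 weeks, with one early and one late week included.
- **Previous scan from day 162:** 2 x 24 weeks plus "1 week for an early assessment + 1 week for a late assessment = 50 weeks".

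The same section derives DFS from actual scan dates rather than nominal visits.

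On baseline timing, Protocol 5.1.1 says: "The baseline assessments should be performed within 28 days prior to study drug initiation". Protocol 4.2 adds: "Patients will take the first dose of study drug within 2 days of randomisation". The important deviations in SAP 2.2, Table 2, include: "Baseline disease assessment performed more than 28 days prior randomization i.e. not performed during screening window". A baseline scan up to four weeks before randomisation is therefore within plan.

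**The concern.** The first branch applies in practice to patients whose only earlier scheduled scan is baseline. Its 25 weeks would fit a baseline scan dated to Day 1, but the wording runs from the scan itself, and the limit has no allowance for the permitted lead of up to 28 days. A patient who misses week 12 and is found to have recurred at week 24 has missed one visit, yet can be treated as having missed two.

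The recurrence then drops out of the primary log-rank test and the patient contributes no follow-up, because censoring goes back to a scan before randomisation. This contradicts the condition that opens the rule. It also differs from the other two branches, which tolerate one missed scan within the visit windows.

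**Working it through.** **Inputs**

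- Limit: 25 weeks = 175 days from the previous assessment (SAP 3.2.1). I take the rule to apply when the gap is more than 175 days, which is the reading kinder to the plan.
- Branch: previous scan before study day 78. Week 12 is study day 85, with a window of 7 days either side (days 78 to 92), so baseline is the only scheduled scan in this branch.
- Lead L: days from the baseline scan to randomisation. A scan 28 days before dosing is 26 to 28 days before randomisation, since dosing starts within 2 days of it. SAP Table 2 accepts up to 28 days.
- Week-24 scan: 161 (earliest), 168 (on time) or 175 (latest) days after randomisation.

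**Step 1. Reproduce the plan's figures.** 2 x 12 + 1 = 25 weeks; 2 x 18 + 1 + 1 = 38 weeks; 2 x 24 + 1 + 1 = 50 weeks. Week 11 is study day 7 x 11 + 1 = 78, and week 23 is study day 7 x 23 + 1 = 162. All agree.

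**Step 2. Longest in-window gap with exactly one scan missed.**

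- Week 12 early to week 48 late: (336 + 7) - (84 - 7) = 266 days = 38.0 weeks; limit 38.
- Week 24 early to week 72 late: (504 + 7) - (168 - 7) = 350 days = 50.0 weeks; limit 50.
- Baseline with L = 28 to week 24 late: 175 + 28 = 203 days = 29.0 weeks; limit 25.

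The first two branches just accommodate one missed scan. The baseline branch falls short by up to 4 weeks.

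**Step 3. Gap when only week 12 is missed.** Gap = days from randomisation to the week-24 scan + L. An asterisk marks a gap over 175 days, where the recurrence is censored.

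| L (days) | Week 24 early (161) | On time (168) | Late (175) |
|---|---|---|---|
| 0 | 161 | 168 | 175 |
| 7 | 168 | 175 | 182* |
| 8 | 169 | 176* | 183* |
| 15 | 176* | 183* | 190* |
| 21 | 182* | 189* | 196* |
| 26 | 187* | 194* | 201* |
| 28 | 189* | 196* | 203* |

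The recurrence is lost from a lead of 15 days (early scan), 8 days (on time) or 1 day (late).

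**Step 4. Where censoring falls.** It falls at the baseline scan. The SAP computes time as the censoring date minus the randomisation date plus 1, so with L = 28 the DFS time is -28 + 1 = -27 days. The Day 1 fallback in SAP 3.2.1 covers patients with no evaluable visit or no baseline data. This patient has both.

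**Step 5. Rough size.** The documents give no distribution of leads and no count of missed week-12 scans, so these are assumptions:

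- Leads spread evenly over 1 to 28 days: 21 of 28 (75%) exceed 7 days.
- 1% to 5% of the 682 randomised patients (Protocol 1.4) miss only week 12: 7 to 34 patients.
- 5% to 10% of those have a recurrence found at an on-time week-24 scan.

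Low end: 7 x 0.05 x 0.75 = 0.3 events. High end: 34 x 0.10 x 0.75 = 2.6 events. That is about 0 to 3.

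**Step 6. After the change.** Counted from randomisation, the gaps are 161 to 175 days. None exceeds 175, so every in-window week-24 recurrence after one missed scan is kept.

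**The case against.** The strongest reply is that Day 1 was always meant. The 25 weeks include a late week but no early week, as if baseline were fixed at Day 1. The next paragraph of SAP 3.2.1 also treats two visits from baseline as 24 + 1 weeks. This is good evidence of intent, and a programmer who started the count at Day 1 would lose nothing. But that paragraph concerns deaths in patients with no evaluable visit or no baseline data. Nothing dates the baseline scan to Day 1 for the missed-visits rule, and the wording points to the scan date.

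Second, the events are recoverable. Attrition-bias sensitivity analysis (c) in SAP 4.3.7.1 uses actual DFS times for such patients. The same section reports reasons for censoring, and off-schedule scans are listed as important deviations. All of this stands. However, analysis (c) also changes the censoring for subsequent therapy, so it does not isolate this effect, and it leaves the primary test as it was.

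Third, formal DFS testing is finished (SAP 7) and the study has been unblinded and reported (Protocol 8.7). That limits the remedy to later analyses and a check of past ones.

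A reader might infer that the lost recurrences fall mainly on placebo and so bias the comparison. The reported hazard ratios imply more DFS events on placebo overall, but the documents give no recurrences by arm around week 24, still less after a missed week-12 scan. If the inference were true, losing placebo events would understate the benefit.

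**Conclusion.** As written, the rule can give a wrong result in the primary analysis: one missed scan is counted as two, and a real recurrence is censored before randomisation. This rests on the literal wording and on actual scan dates. If the programs already start the count at Day 1, no event is lost and only the text needs correcting.

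The effect is conditional and small. It needs a missed week-12 scan, no other evaluable scan before week 24, a recurrence found at week 24, and a lead of at least 8 days if that scan is on time. The 75% in the working applies only to patients with that scan pattern and is not a trial-level rate. A patient who dies with no post-baseline scan falls under the separate clause and is not part of this point.

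About 0 to 3 events under the assumed rates compares with 196 overall DFS events at the second unplanned look (SAP 7): at most 3/196 = 1.5%. A reader might infer that the reported DFS result is in doubt. The documents do not support that: the hazard ratios were 0.17 (99.06% CI 0.11 to 0.26) in stage II-IIIA and 0.20 (99.12% CI 0.14 to 0.30) overall (Protocol 1.4), and a change of this size would not alter the conclusion.

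**What to change.** Add one sentence to SAP 3.2.1: when the previous assessment is the baseline scan, the 25 weeks are counted from randomisation (Day 1), and any resulting censoring is placed at Day 1. Apply it in the remaining exploratory DFS analyses.

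Lengthening the limit to 29 weeks from the scan is not a substitute. With a scan 1 day before randomisation it would run to 203 - 1 = 202 days after randomisation. A patient who missed both week 12 and week 24 and recurred at week 28 (196 days) would then be counted, although the rule is meant to censor that case.

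For analyses already reported, check how the DFS program dated baseline and list any patient censored under this branch. If there are any, give the DFS result with those recurrences restored as a supportive figure and leave the reported test as it is.

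The cost is one sentence, one line in the DFS derivation and one patient listing. Because the study has been unblinded, record the change as a dated clarification with its reason.
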